6.14. Handling of Missing/Incomplete/Inconsistent Data and Time Fields

In the following, 'lower limit' and 'upper limit' refer to the minimum or maximum, respectively, of a possible date. For example, if the day is missing, the lowest limit is the first day of the given month and the upper limit is the last day of the given month. If the day and month are missing, the lower limit refers to the first day of the given year and the upper limit to the last day of the given year. The earliest and the latest dates refer to the first or last date, respectively, when ordered in sequence.

6.14.1. Medical history and baseline disease characteristics

Type of date/time	Date is incomplete	Date is missing
Medical history and baseline disease characteristics	Day missing: 15 th of the month	No replacement
	Day and month missing: 30 th of June	

Statistical Analysis Plan AC-058B202

Type of date/time	Date/time is incomplete	Date/time is missing
EDSS assessment date	 Maximum of lower limit previous scheduled EDSS assessment according to the visit label + 1 day (if available) date of first administration of ponesimod. Unless upper limit is prior to date of first administration of ponesimod, then upper limit 	do not impute and exclude from analysis

6.14.2. EDSS

6.14.3. Relapse

Type of date/time	Date/time is incomplete	Date/time is missing
Relapse start date	Maximum of lower limit and date of first administration of ponesimod Unless upper limit is prior to date of first administration of ponesimod, then upper limit	Date of first administration of ponesimod

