3.11.1.2 Relapses

The clinical parameter "Relapse" includes confirmed and unconfirmed relapses [as defined in Section 3.10.1].

Patients will be instructed to contact their primary investigator / treating neurologist at the clinical site immediately in the event of the appearance of any symptoms suggestive of an MS exacerbation. An unscheduled visit will be organized as soon as possible after onset or worsening of the symptom(s) as follows:

The primary investigator / treating neurologist will examine the patient and decide whether the patient has to be referred to the evaluating neurologist.

In the event of a patient's referral to the evaluating neurologist, the evaluating neurologist will perform the EDSS/FS within 7 days after onset or worsening of the symptom(s).

The decision regarding whether the neurological change is considered as confirmed or unconfirmed relapse will be made by the primary investigator / treating neurologist based on the EDSS/FS scores assessed by the evaluating neurologist.

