5.3.1.1. Annualized relapse rate up to end of Analysis Period

The annualized relapse rate (ARR) is defined as the number of relapses per subject-year.

The following variables are derived for the analysis of ARR:

- Number of confirmed/all relapses with start date in the Analysis Period;
- Length of observation for Analysis Period AP3 expressed in years, defined as: [Analysis Period end date Analysis Period start date + 1] in days, divided by 365.25.

These variables are derived for each subject for the Analysis Period AP3 as defined in Section 5.1.9.

In addition, the number of confirmed relapses in each year in AP3 is derived for each subject (i.e., number of confirmed relapses in first year of ponesimod treatment, number of confirmed relapses in second year of ponesimod treatment, etc.). A year is defined as 365 days for this calculation with only the remaining days counted in the last year, e.g., if a subject has 900 days of follow-up, year 3 for that subject will only have 170 days. A similar analysis for the number of unconfirmed and confirmed (all) relapses will be provided.

For the statistical analysis of ARR, the corresponding logarithm of the length of observation is also derived.

For each Analysis Period, relapses are only considered if the start date of the symptoms \geq date of first intake of ponesimod in that analysis period and \leq end date of that analysis period.

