5.3.1.3. Time to first confirmed/any relapse up to end of the Analysis Period

Time to first confirmed release is derived for AP3 as follows:

The time to first confirmed relapse (in days) is defined as [Date of first confirmed relapse - ponesimod start date + 1] in days.

Subjects without any confirmed relapses during the Analysis Period are censored, and censored time is defined as the Analysis Period end date - ponesimod start date + 1, in days. In the listings censoring is displayed as 'End of Analysis Period' for subjects who did not have a relapse by the end of the Analysis Period. Relapses are labelled as either 'Confirmed Relapses' or 'Unconfirmed Relapses'.

The definition above is also applied for the derivation of time to first 'any' relapse for AP3, i.e., including confirmed and unconfirmed relapses.

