The algorithm is applied by considering the EDSS assessment associated with the relapse (as linked in SDTM) relative to the last EDSS assessment that was performed prior to this linked relapse EDSS assessment and prior to the relapse. The change in EDSS score and corresponding FS scores between these two EDSS assessments is used to define the severity as classified in Table 6 above. If either EDSS assessment is missing, relapse severity is missing.

Duration of relapse (days) is derived as relapse end date – relapse start date + 1 days. Relapses with missing or partially missing end dates are not included.

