- The EDSS assessment is NOT performed during a relapse (between start and end date of a relapse, or if relapse end date is missing, then until start date of relapse + 90 days);
- All available EDSS scores (scheduled or unscheduled, with or without relapse) between the disability accumulation onset and this visit meet the disability accumulation criteria;
- The EDSS confirmation visit may be beyond the end of the Analysis Period, as long as the onset is prior to the end of the Analysis Period.

* Note: In the extension study, visits are scheduled with a time window of +/- 14 days for conducting the EDSS assessment, the minimum per-protocol allowed time difference between two EDSS assessments scheduled 24 weeks apart is 140 days (24 weeks = 168 days minus a 14-day visit time window for each of the 2 visits, i.e., 168 days - 28 days = 140 days).

If an EDSS increase cannot be confirmed due to no available EDSS assessment, but the subject dies due to MS (death with reason 'Multiple sclerosis') the CDA is also considered confirmed, with confirmation date being the death date and onset date of the initial EDSS increase.

- 3. If a confirmation visit cannot be found in step 2, then steps 1 and 2 are repeated to look for the next disability accumulation onset and its confirmation visit. If a confirmation visit is found in step 2, then the algorithm stops for this subject, otherwise steps 1 and 2 are repeated until the last disability accumulation onset is assessed.
- 4. If at none of the assessments a 24-week CDA is identified, but the subject dies due to MS (experiences a relapse with outcome death) the subject is considered to have a 24-week CDA with onset date being the death date.
- 5. Event status and time to event variables for time to event analyses:

After steps 1, 2, 3 and 4 are performed, a subject is considered to have a 24-week confirmed disability accumulation if an accumulation onset with a confirmation visit is found. Otherwise, the subject is considered not to have a 24-week confirmed disability accumulation and is referred to as a censored subject.

For subjects with a 24-week confirmed disability accumulation, the time to event variable (days) is calculated as (onset date – date of first treatment with ponesimod + 1). The onset date is based on the EDSS assessment date rather than the associated nominal visit date.

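### A relapse whose start date is completely missing is dated to the first ponesimod dose, ignoring dates the trial holds; few are likely, but each enters several relapse and disability outputs with wrong values

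*SAP*

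**What the plan says.** SAP 6.14.3 treats two situations in adjacent columns.

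- **Incomplete date.** The start is the "Maximum of lower limit and date of first administration of ponesimod", or the upper limit of the partial date if that falls before the first dose.
- **Completely missing date.** The start is the "date of first administration of ponesimod". Nothing else enters the rule.

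Four derivations use the start date.

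- Time to first confirmed relapse (SAP 5.3.1.3) is "defined as [Date of first confirmed relapse - ponesimod start date + 1] in days". The same formula serves any relapse.
- For the by-year ARR (SAP 5.3.1.1 and 5.3.2.3), "the number of confirmed relapses in each year in AP3 is derived for each subject", with a year taken as 365 days.
- Relapse duration (SAP 5.3.1.5) is end minus start plus 1. It drops relapses with a missing or partial end date, but not those with an imputed start.
- CDA confirmation (SAP 5.3.5.1) requires that "The EDSS assessment is NOT performed during a relapse (between start and end date of a relapse". If the end date is missing, the window is 90 days from the start.

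The start date also decides which period a relapse belongs to: AP3 (SAP 5.3.1.1) or the post-treatment-emergent period (SAP 5.3.1.4).

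**The concern.** AP3 covers the whole ponesimod period, and the protocol (1.3.2.4) gives a median exposure of 8.02 years in the 20 mg group at the interim analysis. Sending an undated relapse to Day 1 can therefore misplace it by many years.

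The trial holds better information. For severity, SAP 5.3.1.5 says "The algorithm is applied by considering the EDSS assessment associated with the relapse (as linked in SDTM"), so a link to an EDSS date exists. Protocol 3.11.1.2 says that, on referral, "the evaluating neurologist will perform the EDSS/FS within 7 days after onset or worsening of the symptom(s"), and Protocol 3.10.1 makes that timing a condition of a confirmed relapse. The source study, the relapse visit and the IV corticosteroid records are also available. Elsewhere the SAP takes more care: an incomplete EDSS date is bounded by the "previous scheduled EDSS assessment according to the visit label + 1 day (if available"), and a completely missing EDSS date is not imputed at all.

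At stake are the outputs that describe durability. Moving an event from a late year to Year 1 makes the late year look better. An artificially long relapse also interferes with CDA confirmation.

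**Working it through.** **Check of the SAP's year arithmetic.** SAP 5.3.1.1 gives 170 days in year 3 for a subject with 900 days of follow-up: 900 − 2 × 365 = 170. This reproduces.

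**One relapse.** Assume a true length of 45 days, a complete end date and a completely missing start. The rule gives start = Day 1, so time to relapse = 1 − 1 + 1 = 1 day, and duration = end day − 1 + 1.

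| True onset | End day | Time to relapse under the rule | Duration under the rule | By-year bin | EDSS visits inside the relapse, true → rule |
|---|---|---|---|---|---|
| Day 547 (mid-year 2) | 591 | 1 day | 591 days | 2 → 1 | 0 → 3 |
| Day 1277 (mid-year 4) | 1321 | 1 day | 1,321 days | 4 → 1 | 0 → 9 |
| Day 2007 (mid-year 6) | 2051 | 1 day | 2,051 days | 6 → 1 | 1 → 18 |
| Day 2737 (mid-year 8) | 2781 | 1 day | 2,781 days | 8 → 1 | 1 → 27 |

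The visit counts are approximate. They take EDSS at weeks 24, 48, 72 and 120 of ponesimod (core week 24, then E7, E9 and E13) and every 12 weeks from week 132.

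If the end date is partial or missing, no duration is derived. If it is missing, the CDA window is only Day 1 to Day 91.

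**By-year ARR.** Shift = k / N for k undated relapses and about N subject-years in Year 1. An upper N follows from 464 randomized 1:1:1:1 in the core study, with placebo patients then split 1:1:1: 464/4 + 464/12 = 116 + 38.7 ≈ 155. A lower N of 110 is assumed. The reference ARR is the protocol's approximate 0.15 for 20 mg.

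- k = 1: 1/155 = 0.0065 to 1/110 = 0.0091, or 4% to 6% of 0.15.
- k = 5: 5/155 = 0.032 to 5/110 = 0.045, or 22% to 30% of 0.15.
- Loss from the true year, for one relapse in year 8 with an assumed 80 to 100 subject-years: 1/100 = 0.010 to 1/80 = 0.0125, or 7% to 8% of 0.15.

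At Day 1 the Kaplan-Meier curve falls by the same k/N: 0.6 to 0.9 points for one subject.

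**Mean relapse duration.** The interim 20 mg figures imply about 0.15 × 817 ≈ 123 relapses. With an assumed mean of 45 days, one 2,781-day record gives (122 × 45 + 2,781)/123 = 67.2 days, 49% above 45. The median would hardly move.

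**CDA.** SAP 5.3.5.1 takes the first scheduled visit at least 140 days after onset that is outside a relapse, with every EDSS in between still meeting the criterion. Visits inside the artificial relapse cannot qualify. A sustained increase is confirmed at a later visit, with the onset date and event time unchanged. It is lost if the EDSS improves before the artificial relapse ends or if no later scheduled visit exists.

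**Period assignment.**

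- SAP 5.3.1.1 counts a relapse in AP3 if it starts on or after first ponesimod intake. An undated core-study relapse in a placebo patient is set exactly to that date and so is counted, although SAP 5.1.9 excludes the placebo period. If it ended before the first dose, its start would follow its end.
- An undated post-treatment relapse moves to Day 1 and leaves the post-treatment ARR.

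**The case against.** **Rarity.** The case may hardly arise. SAP 5.3.1 says start and stop dates are stored for each relapse, relapses have a dedicated form, and monitoring and queries cover the main efficacy endpoints. A confirmed relapse needs an EDSS within 7 days of onset, so one with no onset date sits badly with its own definition. This stands, and it limits the likely size. It is weaker for unconfirmed relapses, which enter the all-relapse analyses without meeting that condition.

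**Convention.** Completely missing AE onsets also go to the first dose (SAP 6.14.4), the event is kept, and an early date is conservative for time to first relapse. That is fair for that one endpoint. It is not conservative for later-year ARR or CDA. For AEs, SAP 5.4.3.1 also checks whether the end date shows a pre-treatment event; relapses have no such check.

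**Visibility.** All objectives are exploratory and every relapse is listed, so a relapse of several years would be seen. True, but the tables would still be built on the imputed date.

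A reader might infer more than the documents support:

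- **That the incomplete-date rule does the same.** It shifts onset by at most 30 days when the day is missing, and by less than a year when day and month are missing.
- **That every undated relapse lasts years.** Duration needs a complete end date, and a long CDA window needs a recorded one.
- **That CDA is blocked for good.** Confirmation is delayed and only sometimes lost.
- **That overall AP3 ARR is biased.** It is unchanged for relapses truly in AP3.

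**Conclusion.** The rule for completely missing relapse start dates gives wrong values and is worth changing. Each affected relapse has a time to relapse of 1 day and moves to Year 1. With a complete end date its duration runs from Day 1. With a recorded end date it bars CDA confirmation up to that date. Placebo-period and post-treatment relapses can be placed in the wrong period.

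The total effect cannot be stated, because the documents do not count undated relapses; it is probably small, especially for confirmed relapses. The sizes above rest on assumed group sizes, an assumed 45-day relapse and the interim 20 mg figures. By-year ARR is sensitive only if several such records exist. Mean duration is sensitive to a single one.

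**What to change.** Leave the incomplete-date rule in SAP 6.14.3 as it is. For a completely missing start:

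1. Impute the linked relapse EDSS date minus 7 days. If there is no linked EDSS, use the relapse visit or the IV corticosteroid start date. Never go later than the relapse end date. Fall back on the first-dose date only if none of these exists.
2. Keep the first-dose date as a floor, as the incomplete-date rule does, unless the relapse ended earlier. SDTM201 relapses of placebo patients stay out of AP3 unless shown to start on or after the first ponesimod dose.
3. Flag imputed starts and exclude them from relapse duration.
4. In the CDA rule, limit the relapse window to at most 90 days when the start date was completely missing.

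A rule that simply took the latest of several candidate dates would not do: without a cap it could place the start after the relapse end.

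The cost is SAP wording, a few lines of derivation and a slightly smaller denominator for duration. No new data are needed. Reporting the number of imputed starts would show whether the issue mattered.

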6.14.4. Adverse event onset and resolution dates

The following imputation rules are applied for (partially missing) AE onset dates:

- Onset day missing:
 - If month and year put the event start date clearly on or after month and year of first administration of ponesimod in the Analysis Period, and clearly on or before the month and year of date of last administration of ponesimod in the Analysis Period + 15 days, the event is considered to be treatment-emergent, unless event occurred during pregnancy interruption as described in Section 5.1.4.
 - If the month and year correspond to the month and year of first administration of ponesimod in the Analysis Period, impute onset date of the AE as the date of the first administration of ponesimod in the Analysis Period.
 - If the month and year are clearly after the month and year of date of first administration of ponesimod in the Analysis Period, the onset date is imputed as the maximum of (date of Study Day 2, 1st day of the month and year given.

CONFIDENTIAL - FOIA Exemptions Apply in U.S.

- If event onset month and year are clearly prior to the month and year of date of first administration of ponesimod in the Analysis Period, the onset date is imputed to the last day of the given month.
- Onset day and month missing:
 - If the year is the same year as the year of first administration of ponesimod in the Analysis Period or later, and if the year is prior to or in the same year as the date of last administration of ponesimod in the Analysis Period + 15 days, the event is considered to be treatment-emergent unless event occurred during pregnancy interruption as described in Section 5.1.4.
 - If the year is clearly on or after the year of first administration of ponesimod in the Analysis Period, the onset date is imputed as date of maximum of (Study Day 2, 1 January of the given year).
 - If the event onset year is clearly prior to the year of first administration of ponesimod in the Analysis Period, the onset date is imputed to 31-December of the given year.
- Onset date is completely missing:
 - The event is considered to be treatment-emergent.
 - The onset date is imputed as date of first administration of ponesimod in the Analysis Period.
- Resolution day missing:
 - If event resolution month and year are clearly prior to the month and year of the date of last administration of ponesimod in the Analysis Period, the resolution date is imputed to the last day of the given month.
 - If event resolution month and year are the same as the month and year of the date of last administration of ponesimod in the Analysis Period, the resolution date is imputed to date of last administration of ponesimod in the Analysis Period, and the event is considered to be ongoing.
 - If event resolution month and year are clearly after the month and year of the last ponesimod administration (EOT), the resolution date is imputed to the last day of the given month.
- Resolution day and month missing:
 - If event resolution year is clearly prior to the year of the date of last administration of ponesimod in the Analysis Period, the resolution date is imputed to 31-December of the given year.
 - If event resolution year is the same as the year of the date of last administration of ponesimod in the Analysis Period, the resolution date is imputed to date of last administration of ponesimod in the Analysis Period, and the event is considered to be ongoing.
- Onset date is on a date subsequent to the resolution date:
 - If event start date occurs at a date after the event resolution date, the event is considered to be treatment-emergent. However, neither the onset date nor the resolution date is changed.

CONFIDENTIAL – FOIA Exemptions Apply in U.S.

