5.4.3. Adverse Events

An AE is any event reported by the investigator on the CRF. All adverse events are stored in the appropriate SDTM.AE domain.

AEs collected in the core study are stored in SDTM201.AE. New AEs collected in the extension study are stored in SDTM202.AE, together with follow-up of AEs that were ongoing at the end of the core study. The two AE datasets are concatenated for the purposes of this analysis, and the additional follow-up details collected for AEs that were ongoing at the time of the end of the core study are merged onto the original records to create a single record for each such AE.

All AEs reported in both SDTM201.AE and SDTM201.AE are coded to the MedDRA version 26.0.

Adverse events with a missing end date are considered as ongoing, i.e., the end date is set to missing.

5.4.3.1. Duration of AE (days) is derived as min [AE end date, EOS date] – AE start date + 1 day. Treatment-emergent adverse events

Treatment-emergent adverse events (TEAEs) are defined according to the general definition of treatment-emergent for safety variables as described in Section 5.1.4.

AEs with completely missing start date will be considered as treatment-emergent unless it is otherwise clear (e.g., by end date) that the event occurred pre-treatment. If it is not clear whether the event is treatment-emergent or not (in case of partial dates), the event will be considered a TEAE if the AE start date is potentially on or after treatment start date. For example, an AE with partial date of "May 2016" and a treatment start date of "23 May 2016" is considered treatment-emergent. For imputation of partial dates see definition in Section 6.14.4.

AEs with an onset date during treatment interruptions (including periods between studies and study-periods) except the period of planned pregnancy interruptions (see Section 5.1.4) are considered treatment-emergent.

AEs considered treatment-emergent are flagged in the AdaM dataset.

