5.4.3.2. Post-treatment-emergent adverse events

Post-treatment-emergent adverse events are defined as those AEs occurring from 16 days after last administration of ponesimod until last study date, i.e., AEs occurring during the post-treatment-emergent period (Section 5.1.6)

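### SAP 6.14.4 sets a partial AE resolution date in the month or year of the last dose to the last-dose date; for AEs with a known later onset this inverts the dates and, read literally, can make post-treatment AEs treatment-emergent

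*SAP*

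**What the plan says.** SAP 6.14.4 lists rules for partial AE resolution dates.

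- Day missing, month before or after that of the last dose: last day of the recorded month.
- Day missing, same month and year as the last dose: "the resolution date is imputed to date of last administration of ponesimod in the Analysis Period, and the event is considered to be ongoing".
- Day and month missing: the same wording applies "If event resolution year is the same as the year of the date of last administration of ponesimod in the Analysis Period". An earlier year goes to 31 December.

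The list ends with a rule for inverted dates: "If event start date occurs at a date after the event resolution date, the event is considered to be treatment-emergent". It adds: "However, neither the onset date nor the resolution date is changed". It does not say whether it applies only to dates as recorded or also to dates imputed a few lines earlier.

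Elsewhere, 5.1.4 ends the treatment-emergent period 15 days after the last dose, 5.1.6 starts the post-treatment-emergent period on day 16, and 5.4.3.2 has post-treatment-emergent AEs "defined as those AEs occurring from 16 days after last administration of ponesimod until last study date". Section 5.4.3 says: "Adverse events with a missing end date are considered as ongoing, i.e., the end date is set to missing". Section 5.4.3.1 computes duration as the earlier of end date and EOS date, minus start date, plus 1.

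For an onset date that is completely missing, 6.14.4 says without qualification that "the event is considered to be treatment-emergent". Section 5.4.3.1 instead treats such an AE as "treatment-emergent unless it is otherwise clear (e.g., by end date) that the event occurred pre-treatment".

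**The concern.** The branch for the last-dose month or year is the odd one out. Its neighbours take the latest date the record allows; this one moves the date back to the last dose, with nothing to keep it on or after onset. It then labels the event ongoing although the site recorded a month or year of resolution and although outcome is held separately in AEOUT (5.4.3.5).

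Protocol 4.2.4.2 collects AEs until 30 or 90 days after the last dose, so onsets after the last dose are expected. For those the rule produces a resolution before onset. If the inverted-date bullet is then applied to the result, an AE whose onset is known and lies outside the 15-day window is flagged treatment-emergent.

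Such an AE still meets the 5.4.3.2 definition, so it could be counted in both the treatment-emergent and the post-treatment tables. In the rates per 100 subject-years it would add an event without time, because 5.4.4.2 stops observation time at last dose + 15 days.

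**Working it through.** The plan states no figure here to reproduce. The check applies the written rules to dates.

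**Inputs.** L = last-dose date (only AP3 is analysed, so this is the last ponesimod dose overall). Onset = L + k, fully known. Window: treatment-emergent if k ≤ 15 (5.1.4). Duration = min(end, EOS) − start + 1 (5.4.3.1).

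**Duration.** In the matching month or year the imputed end is L. L is not later than EOS, so the cap does not bind. Duration = L − (L + k) + 1 = 1 − k. It is 0 at k = 1 and negative from k = 2.

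**Cases.**

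| Case | Last dose | Onset (k) | Recorded resolution | Imputed end | Duration | By 5.1.4 | After inverted-date bullet |
|---|---|---|---|---|---|---|---|
| A | 5 Mar 2021 | 25 Mar (20) | Mar 2021 | 5 Mar | −19 | post-treatment | treatment-emergent |
| B | 5 Mar 2021 | 10 Mar (5) | Mar 2021 | 5 Mar | −4 | treatment-emergent | unchanged |
| C | 5 Mar 2021 | 20 Apr (46) | 2021 | 5 Mar | −45 | post-treatment | treatment-emergent |
| D | 20 Mar 2021 | 2 Mar (−18) | Mar 2021 | 20 Mar | 19 | treatment-emergent | unchanged |
| E | 5 Jan 2022 | 15 Mar (69) | 2022 | 5 Jan | −68 | post-treatment | treatment-emergent |

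Dates invert only when k ≥ 1. The flag changes only when k ≥ 16. In case D the only oddity is the ongoing label.

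**Which calendar combinations can trigger a change of flag.** Take a 365-day year and onsets on days 16 to 90 (75 days), giving 365 × 75 = 27,375 pairs of last-dose date and onset day.

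- Month rule: in a month of M days the last dose must fall on day M − 16 or earlier. That is 7 × 15 + 4 × 14 + 12 = 173 of 365 last-dose dates (47%). Pairs: 7 × 120 + 4 × 105 + 78 = 1,338, or 4.9%.
- Year rule: 365 − 16 = 349 of 365 last-dose dates. Pairs: 275 × 75 + (74 × 75)/2 = 20,625 + 2,775 = 23,400, or 85%.

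These are shares of calendar combinations, not expected counts of AEs.

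**Under the rule proposed below** (assuming, for illustration, EOS at last dose + 90 days):

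- A: end 31 Mar, 7 days, post-treatment.
- B: end 31 Mar, 22 days, treatment-emergent.
- C: end 31 Dec 2021, duration capped at EOS (3 Jun) = 45 days, post-treatment.
- D: end 31 Mar, 30 days, treatment-emergent.
- E: end 31 Dec 2022, duration capped at EOS (5 Apr) = 22 days, post-treatment.

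No inversion and no change of flag remains.

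**The case against.** The strongest reply is that the change of flag needs the inverted-date bullet to act on dates that 6.14.4 has itself imputed. The SAP gives no order of rules. The section title covers inconsistent as well as missing data, and a bullet that leaves both dates unchanged reads naturally as one about recorded dates. If that was meant, or if ongoing means that the end date is left missing, no AE is reclassified. This stands as a plausible intention, but the text says neither, and the inversion and negative duration occur regardless of it.

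A second reply is that calling doubtful events treatment-emergent is the SAP's general conservative policy: missing intensity counts as severe, missing relationship as related, missing seriousness as serious. That is fair where onset is uncertain. It does not justify overriding a known onset outside the window.

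Third, the clash with 5.4.3 over the word ongoing is not strict. That section says that a missing end date makes an AE ongoing, not that nothing else can, and 6.14.4 might mean ongoing at the last dose. The label is then ambiguous, but it still needs defining or removing.

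Fourth, the missing-onset bullet can be read as shorthand for 5.4.3.1, which already contains the pre-treatment exception. That makes it an alignment point only.

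**Conclusion.** The rule as written gives impossible dates for AEs with a partial resolution date in the last-dose month or year and a known onset after the last dose. Read literally, it also gives the wrong treatment-emergent flag when that onset is 16 or more days after the last dose. The second step rests on the unstated order of rules. The documents do not give the share of partial resolution dates. The number of affected AEs is probably small, and all objectives are exploratory.

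A reader might infer more than the documents support:

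- That every AE resolving around the last dose is affected. Only partial resolution dates trigger the rule.
- That every follow-up AE with a year-only resolution changes status. Onsets up to day 15 are already treatment-emergent, and a partial onset that could fall within the window already is too.
- That AEs leading to discontinuation are misclassified. They normally start on or before the last dose, as in case D, and keep their status.
- That summary tables would report wrong durations, or that listings would show an AE as both resolved and ongoing. No planned AE summary uses duration, and the SAP does not say that listings print imputed dates.

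It is worth correcting because 5.4.4.3.3 plans dedicated post-treatment AE tables and a CRO programs the AE analyses from this text, so two programmers could reasonably produce different flags.

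**What to change.** In SAP 6.14.4:

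1. Impute a partial resolution date in the last-dose month or year to the last possible date of the recorded month or year, never before onset. The year-only list has no branch for a year after the last dose, and the same rule would fill that gap.
2. Do not cap the imputed date at EOS. Section 5.4.3.1 already caps duration there. Capping the date could place a resolution before its recorded month: with EOS on 10 December 2022 and resolution in January 2023, the date would become 10 December. Such dates can arise because Protocol 4.3.3 follows SAEs ongoing at EOS until resolution or stabilization.
3. Delete the statement that the event is ongoing from both branches and take status from AEOUT.
4. Restrict the onset-after-resolution rule to recorded dates. Whenever onset is known, let it decide treatment-emergent status under 5.1.4. Default to treatment-emergent only when onset cannot be placed.
5. Carry the pre-treatment exception of 5.4.3.1 into the missing-onset bullet.

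The cost is a few lines of SAP text and a small change to the adverse event analysis dataset. No new data are needed.
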